2. PROTOCOL SUMMARY

2.1. Synopsis

PRODUCT NAME/NUMBER	Tamoxifen vaginal insert / DARE-VVA1: 1, 5, 10, 20 mg
PROTOCOL NUMBER	DARE-VVA-001
DEVELOPMENT PHASE	Phase 1/2
PROTOCOL TITLE	Phase 1/2 Study of Intravaginal Tamoxifen (DARE-VVA1): Randomized, Double-blind, Placebo-controlled Study of Safety, Pharmacokinetics and Pharmacodynamics in Postmenopausal Participants with Moderate to Severe Vulvar and Vaginal Atrophy
INDICATION	Moderate to severe vulvar and vaginal atrophy (VVA)
OBJECTIVES	
Primary:
 
 To evaluate the safety and tolerability of DARE-VVA1 by intravaginal administration To determine the plasma pharmacokinetics (PK) of DARE-VVA1 after intravaginal application 
Secondary:
 
 To evaluate preliminary efficacy and pharmacodynamics (PD) of DARE-VVA1 in terms of most bothersome symptom, dyspareunia, and changes in vaginal cytology and pH 
Exploratory:
 
 To evaluate the impact of DARE-VVA1 on quality of life using a menopause-specific instrument To assess the usability and acceptability of DARE-VVA1
RATIONALE	The use of estrogen-containing products for the treatment of VVA is contraindicated in women with hormone receptor-positive (HR+) breast cancer due to their capacity to promote tumor growth. There remains a large unmet need for a novel nonhormonal VVA treatment for this subset of cancer patients and survivors, and other women who require or prefer a treatment option that does not contain estrogen. An exploratory study of intravaginal tamoxifen has demonstrated the potential for this selective estrogen receptor modulator (SERM), which acts as an estrogen receptor agonist in the vagina and as an antagonist in breast tissue, to improve VVA symptoms. The present study will evaluate different doses of DARE-VVA1, a tamoxifen vaginal insert, in postmenopausal women with VVA, including women with a history of breast cancer, to evaluate safety and tolerability, PK, initial responses to treatment, and PD.
STUDY DESIGN	
This is a randomized, multi-center, double-blind, parallel-arm, placebo-controlled, dose-ranging study to evaluate the safety, tolerability, PK, and PD of DARE-VVA1, a novel intravaginal tamoxifen product. The investigational product (IP) will be evaluated at 4 dose levels (1 mg, 5 mg, 10 mg, and 20 mg) and compared to a placebo vaginal insert. The IP will be administered intravaginally for 56 days according to the following treatment schedule: once daily for 2 weeks then twice a week for 6 weeks.
 
Approximately 40 postmenopausal women with VVA will be enrolled, 20 who have undergone hysterectomy and 20 who have not. After signing informed consent, eligible

	
participants will be randomly allocated as follows: the 20 hysterectomized women will be allocated to 1 of the 5 treatment groups, and the 20 non-hysterectomized women will be randomly allocated to one of the same 5 treatment groups, such that each treatment group ends up with 4 hysterectomized women and 4 non-hysterectomized women, for a total of 8 women. In each treatment group, participants will have serial blood sampling for PK analysis and undergo safety evaluations and preliminary assessments of effectiveness.
 
Following the completion of treatment, participants will attend a follow-up visit on Day 63.
																		

PLANNED NUMBER OF PARTICIPANTS
	
A sufficient number of participants will be screened to randomize 40 participants (8 participants per group) to the following planned treatment groups:
 
  
 Dose Level	Treatment	Number of Participants	
   
 Placebo	One placebo insert	N=8	
 
 1 mg	One DARE-VVA1 1 mg insert	N=8	
 
 5 mg	One DARE-VVA1 5 mg insert	N=8	
 
 10 mg	One DARE-VVA1 10 mg insert	N=8	
 
 20 mg	One DARE-VVA1 20 mg insert	N=8	
  
	Dose Level	Treatment	Number of Participants	Placebo	One placebo insert	N=8	1 mg	One DARE-VVA1 1 mg insert	N=8	5 mg	One DARE-VVA1 5 mg insert	N=8	10 mg	One DARE-VVA1 10 mg insert	N=8	20 mg	One DARE-VVA1 20 mg insert	N=8
Dose Level	Treatment	Number of Participants																	
Placebo	One placebo insert	N=8																	
1 mg	One DARE-VVA1 1 mg insert	N=8																	
5 mg	One DARE-VVA1 5 mg insert	N=8																	
10 mg	One DARE-VVA1 10 mg insert	N=8																	
20 mg	One DARE-VVA1 20 mg insert	N=8																	

STUDY ENTRY CRITERIA
	
This study will enroll healthy postmenopausal females with moderate to severe VVA.
 
Participants must meet all inclusion criteria to be eligible for enrollment into the study. Participants will not be eligible for entry into this study if they meet any of the exclusion criteria and will be discontinued at the discretion of the investigator in consultation with the medical monitor if they develop any of the exclusion criteria during the study.
 
Inclusion criteria:
 
 1. Women aged 40-75 (inclusive). 2. Postmenopausal women with a body mass index between 18 and 38 kg/m², inclusive. 3. Postmenopausal, defined as: 
 a. For non-hysterectomized women, 12 months of spontaneous amenorrhea or 6 months of spontaneous amenorrhea with serum follicle-stimulating hormone (FSH) levels > 40 mIU/mL or 6 weeks postsurgical bilateral oophorectomy. b. For hysterectomized women, serum follicle-stimulating hormone (FSH) levels > 40 mIU/mL or 6 weeks postsurgical bilateral oophorectomy. 4. Have moderate to severe VVA as determined by self-assessment of the following symptoms: vaginal dryness, vaginal and/or vulvar irritation/itching, dysuria, vaginal pain with sexual activity (dyspareunia) (all self-assessed as none, mild, moderate, or severe), or vaginal bleeding associated with sexual activity (self-assessed as presence versus absence). To be eligible, at least 1 of the first 4 symptoms must be reported as moderate or severe, or vaginal bleeding associated with sexual activity must be present. 5. Women who currently have vaginal intercourse or other sexual activity (masturbation, etc.) at least once a month (with or without a partner), or who had intercourse or other sexual activity at least once a month in the past, but later decreased sexual activity due to excessive pain or vaginal dryness. Participants must be willing to engage in vaginal intercourse or other sexual activity (masturbation, etc.) at least 1 time between Days 49-56 of the clinical study. 																		

	
6. Participants, upon pelvic examination with speculum examination, must have a normal-appearing vulva other than atrophic changes and normal-appearing vagina (without erosions, ulcerations, scarring, or evidence of dermatoses) other than atrophic changes (loss of rugae, mucosal pallor, mucosal dryness, mucosal petechiae). Women without a cervix must have a normal-appearing vaginal cuff.
 
7. Women who have not undergone hysterectomy must have:
 
 a. No prior history of endometrial ablation. b. Endometrial thickness ≤ 4 mm on transvaginal ultrasound. 
8. Women with a cervix must:
 
 a. Have a normal-appearing cervix other than atrophic changes (i.e., cervical stenosis and/or flushness with the vaginal wall). b. Be current on all recommended screening and management requirements for cervical cancer. 
9. Vaginal cellular cytology with $\leq 5\%$ superficial cells.
 
10. Vaginal pH > 5 at Screening Visit.
 
11. Normal mammogram report within 2 years of screening.
 
12. Normal manual breast examination by investigator at baseline.
 
13. Baseline hematology, clinical chemistry, urinalysis, coagulation, and viral serologies for human immunodeficiency virus (HIV), hepatitis C virus (HCV), and hepatitis B surface antigen (HBsAg) all within normal limits OR accepted by the investigator and medical monitor as not clinically significant.
 
14. Normal 12-lead electrocardiogram (ECG).
 
15. Able to read, understand, and provide written informed consent and applicable data protection authorization after the nature of the study has been fully explained, and must be willing to comply with all study requirements.
 
16. Willing and able to correctly and independently complete all study procedures.
 
Exclusion criteria:
 
 1. A history of or physical examination finding for any significant cardiovascular, renal, pulmonary, neurological and hepatic diseases preventing compliance with this study. 2. A medical history of or use of anticoagulant drugs to treat or prevent coagulopathies, thrombophilia or thromboembolic disease (deep vein thrombosis, pulmonary or systemic embolism, stroke, or transient ischemic attack). 3. Uncontrolled hypertension (either systolic > 180 mmHg or diastolic > 105 mmHg), treatment with Class 1 antiarrhythmics or digitalis, history of congestive heart failure (New York Heart Association [NYHA] $> Class I$), or myocardial infarction within 12 months. 4. Women with a cervix cannot have had an abnormal cervical screening test within 2 years of screening. Participants can have atypical squamous cells of undetermined significance if human papilloma virus-negative. 5. Women who have not undergone hysterectomy cannot have a history of or current endometrial pathology: hyperplasia, carcinoma and/or polyp (prior history of a benign endometrial polyp with no current evidence of polyp is acceptable).
--	--

	
6. A medical history of breast cancer within 5 years of screening.
 
Participants with a history of breast cancer more than 5 years prior to screening are considered eligible if their disease was node-negative, nonmetastatic, and if all treatment with aromatase inhibitors (AIs) or SERMs was completed at least 6 months prior to screening.
 
7. A medical history of malignant melanoma .
 
8. Any cancer (except nonmelanomatous skin cancer) diagnosed less than 5 years prior to the Screening Visit.
 
9. A medical history of undiagnosed vaginal bleeding.
 
10. A known or suspected estrogen-dependent neoplasia.
 
11. Previous radiation treatment to the pelvis.
 
12. Women who have previously reported an unsatisfactory outcome from a vaginal hormone therapy for VVA.
 
13. Known hypersensitivity to any ingredients in DARE-VVA1.
 
14. Use of vaginal hormonal products (rings, creams, gels, tablets, capsules) within 4 weeks prior to Day 1.
 
15. Use of transdermal estrogen products within 4 weeks prior to Day 1.
 
16. Use of oral estrogen therapy within 8 weeks prior to Day 1.
 
17. Use of estrogen-alone injectable drug therapy within 12 weeks prior to Day 1.
 
18. Administration of estrogen pellet therapy within 6 months prior to Day 1.
 
19. Use of thyroid hormone replacement therapy unless the participant is on a stable dose for > 6 months, and participant is euthyroid based on a normal, sensitive immunoassay for thyroid-stimulating hormone (TSH).
 
20. Use of SERMs or AIs within 6 months prior to screening.
 
21. Use of anabolic or other steroids (including hormonal creams such as testosterone) within 4 weeks prior to Day 1.
 
22. Use of corticosteroids, > 5 mg/day prednisone or equivalent, for more than 4 weeks within 4 weeks prior to Day 1.
 
23. Participants with any self-reported active sexually transmitted disease and/or evidence of infection (including bacterial vaginosis) on vaginal examination by the investigator.
 
24. Participants with a urinary tract infection during screening as assessed by urine dipstick test with abnormal test findings (any positive result for leukocytes AND any positive result for nitrites).
 
25. Women who have not undergone hysterectomy cannot have clinically significant uterine fibroids.
 
26. Evidence of current alcohol or drug abuse in the past 60 days, including a positive result from the urine drugs of abuse or alcohol screen, or history of drug or alcohol dependence in the last 2 years, as assessed by the investigator. Alcohol abuse is defined as greater than 14 standard units/week for females, and drug abuse is defined as known psychiatric or substance abuse disorder that would interfere with participation with the requirements of this study, including current use of any illicit drugs. Use of medical cannabis is not exclusionary.

--	---

	
27. Participation in any other investigational drug or device trial in which administration of an investigational study drug/device occurred within 30 days or placement of a non-drug eluting medical device within 15 days prior to the Screening Visit (Visit 1).
 
28. In the opinion of the investigator, participant has any disorder or finding that might interfere with the conduct of the study.

TEST PRODUCT	
Name: DARE-VVA1 (tamoxifen vaginal insert) 1, 5, 10, and 20 mg
 
Dose, route: 1, 5, 10, and 20 mg; vaginal administration by self-placement

CONTROL PRODUCT	
Name: Matching placebo vaginal insert
 
Dose, route: vaginal administration by self-placement

TREATMENT REGIMENS	
DARE-VVA1 and placebo inserts will be self-administered by participants for 56 days (Days 1 to 56). The IP will be inserted intravaginally in the morning, at approximately the same time. Treatment will be administered once a day for the first 2 weeks, followed by twice weekly treatment for 6 weeks. The first twice-weekly dose will be administered on Day 18 during a study visit.

PLANNED STUDY SITES	
Approximately 3 study sites in Australia.

CRITERIA FOR EVALUATION	
Pharmacokinetics:
 
After baseline evaluations including the time 0 venous plasma sample, the Day 1 DARE-VVA1 dose or matching placebo will be administered. Serial peripheral venous samples will be drawn from an indwelling line at 0.5, 1, 2, 4, 5, 8, 12, and 24 hours. The same sampling schedule will be used for PK analysis with administration of the Day 56 vaginal insert. Trough samples will be collected before administration of inserts on Days 4, 7, 10, 18, 28, and 42, and a final sample will be collected at follow-up on Day 63.
 
Samples will be analyzed using validated methods to determine plasma concentrations of tamoxifen and 3 metabolites: 4-hydroxytamoxifen, N-desmethyltamoxifen, and N-desmethyl-4-hydroxytamoxifen (endoxifen).
 
Safety:
 
Observations of safety (self-reported or by examination) will be recorded on an ongoing basis. Any irritation, discharge or pain will be reported as an adverse event (AE) using standardized Medical Dictionary for Regulatory Activities (MedDRA) codes and graded for severity.
 
Visual examination by vaginal speculum and full pelvic examination for any vaginal inflammation will be conducted at screening, pretreatment (Day 1), during treatment, and 1 week after treatment.
 
Clinical laboratory measurements including full hematology and biochemistry panels will be recorded at screening, at baseline, on Days 7, 18, 28, and 57, and 1 week after treatment.
 
Dipstick urinalysis of a void sample will be reported at screening, at baseline, on Days 7, 18, 28, and 57, and 1 week after treatment. If abnormal, the sample will be centrifuged for microscopic description of cellular elements.
 
Vital signs, including pulse rate, respiratory rate, and supine blood pressure, will be recorded in a supine position at screening, during the administration period, and 1 week after treatment.
 
Standard 12-lead ECGs will be recorded at screening, prior to dose on Days 1, 7, 18, 28, and 56, at 4 hours postdose on Days 1 and 56, on Day 57, and 1 week after treatment.

	
A complete physical examination (excluding rectal examinations) will be performed at screening and will include a manual breast examination. Subsequent physical examinations will be abbreviated and will be directed based on signs and symptoms exhibited by the participant.
 
Pelvic speculum and visual examinations will be conducted to identify vaginal abnormalities. Clinically significant abnormal findings from the speculum examination will be reported as an AE. Investigators will also conduct an assessment of local irritation; erythema and edema will be rated from 0 (none) to 3 (severe).
 
Women who have not undergone hysterectomy will have a transvaginal ultrasound to determine endometrial thickness.
 
Pharmacodynamics and Efficacy:
 
Estrogenic effect measurements will include vaginal cytology (maturation index; percentage of basal and superficial cells) and vaginal pH at screening and baseline, every 2 weeks during treatment, and 1 week after treatment.
 
Pharmacodynamics will be assessed by correlating the dose administered to exposure of tamoxifen in plasma, and then by relating the exposure to local vaginal changes in cytology and pH as well as to the reported symptomatology over 56 days.
 
Exploratory:
 
Menopause-specific Quality of Life (MENQOL) questionnaires will be completed prior to dosing on Day 1, and after treatment on Day 57.
 
Details of the analysis of the responses to the Usability and Acceptability questionnaire will be outlined in the statistical analysis plan.

STATISTICAL METHODS	
General:
 
For the purpose of all safety, efficacy, and other analyses where applicable, baseline is defined as the last measurement before the start of study drug administration.
 
Continuous endpoints will be summarized with number (n), mean, standard deviation, median, minimum, and maximum. In addition, change from baseline values will be calculated at each time point and summarized descriptively. For categorical endpoints, descriptive summaries will include counts and percentages.
 
Analysis Populations:
 
The ITT population, defined as all randomized participants, will be used to summarize participant disposition, demographics and baseline characteristic summaries, efficacy endpoints, and exploratory endpoints.
 
Efficacy evaluations include changes in vaginal pH, changes in vaginal cytology (maturation index; percentage of basal and superficial cells), change in dyspareunia, and change in most bothersome symptom. These will be summarized using the ITT population. For the analysis the exploratory endpoints, results from the MENQOL questionnaire and the Usability and Acceptability questionnaire will be summarized over time from baseline in the ITT population.
 
An analysis of covariance (ANCOVA) model will be used to assess treatment differences in change from baseline for vaginal pH, vaginal cytology, and most bothersome symptom, using baseline score as a covariate. With no formal testing planned for this study, the P values will be informational.
 
The Safety population, defined all participants who are enrolled and receive any amount of planned IP, will summarize the recorded AEs, clinical laboratory safety tests, vital signs, ECG results, physical examination findings, and any other parameter relevant for safety assessment.

	
The PK population consists of all participants who receive at least 1 dose of IP and provide at least 1 quantifiable PK plasma sample. This population will be used to summarize PK concentrations and parameters over time.
 
Pharmacokinetic parameter estimates will be calculated by a standard noncompartmental method of analysis; these may include (but are not limited to) measures of the extent of absorption using estimates of the area under the plasma concentration-time curve (AUC), the maximum observed drug concentration (C_{max}), and the time to reach maximum drug concentration (T_{max}). Other parameters may be included at the discretion of the pharmacokineticist and as data permit.
 
Participant listings will be provided for all the CRF data.

SAMPLE SIZE DETERMINATION	
This dose ranging study is not powered for statistical significance. A sample size of 8 participants in each treatment group is considered sufficient to provide information on safety, PK, and PD effects, to guide the design of future studies with DARE-VVA1. A total of 40 participants is planned for this study.

STUDY AND TREATMENT DURATION	
The sequence and maximum duration of the study periods will be as follows:
 
 1. Screening: 21 days 2. Treatment: 56 days 3. Follow-up: 7 days 
The maximum treatment duration for each participant is 56 days. The maximum study duration for each participant is approximately 12 weeks.

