In the present study, steps will be taken to reduce the risks associated with the use of tamoxifen. In addition to limiting the treatment duration to 56 days, and to the reduction of systemic exposure afforded by the use of intravaginal administration, the present study has been designed with eligibility criteria that will exclude participants who might be at particular risk of experiencing the more serious side effects of tamoxifen, while regular safety monitoring will be performed. Eligible participants who have not undergone hysterectomy will have no history of endometrial ablation or endometrial hyperplasia, with ultrasound at screening showing endometrial thickness ≤ 4 mm. Participants with a cervix will also have an up-to-date cervical cancer screening record. All participants must have a normal mammogram within 2 years of screening; participants who have not had a mammogram in the last 2 years, or have a cervix but have not had a cervical screening test (CST) in the last 5 years, will be required to undergo these assessments during screening.

Participants will be excluded if they have any of the following: a history of coagulopathies, thrombophilia, thromboembolic disease, or significant transient ischemic attack; significant cardiac history; recent history of breast cancer (or suspicion of breast cancer), abnormal cervical screening result within 2 years; endometrial pathology; known or suspected estrogen-dependent neoplasia. Safety monitoring will include 12-lead electrocardiograms (ECGs) to evaluate possible cardiac problems; laboratory assessments will include measurement of liver functions tests and clotting parameters, to monitor hepatic safety and potential embolism/thrombotic events, respectively; and regular vaginal inspection. Due to the reported risks of endometrial adenocarcinoma and uterine sarcoma, transvaginal ultrasounds will be performed at screening on women who have not undergone hysterectomy in order to measure endometrial thickness.

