participants who have not had these tests in the timeframe indicated by the inclusion criteria. Participants will not be eligible if they have a medical history that suggests that they may be at risk of serious side effects of tamoxifen (e.g., thromboembolic disease, abnormal cervical screening results or history of endometrial pathology). Participants will also be excluded if they are receiving medications that could confound assessments (e.g., vaginal hormonal products, estrogen therapy, or use of SERMs or AIs within 6 months prior to screening) or have previously experienced an unsatisfactory outcome from a vaginal hormone therapy for VVA.

Preliminary efficacy will be assessed by vaginal cytology (for maturation index) and by vaginal pH, measured at baseline, every 2 weeks during treatment, following completion of treatment (Day 57), and at the follow-up visit conducted on Day 63. In addition, most bothersome symptom and dyspareunia will be evaluated during the treatment period and at follow-up. An exploratory assessment of quality of life will be conducted using the Menopause-specific Quality of Life (MENQOL) questionnaire, and participants will report on the usability and acceptability of DARE-VVA1 using a questionnaire.

In each treatment group, participants will have serial blood sampling for PK analysis, with venous samples drawn from an indwelling line. Dense sampling will be performed following the Day 1 and Day 56 administrations of DARE-VVA1; trough samples will be collected prior to dosing on Days 4, 7, 10, 18, 28, and 42, and a final sample will be collected at follow-up on Day 63. Samples will be analyzed using validated methods to determine plasma concentrations of tamoxifen and 3 metabolites: 4-hydroxytamoxifen, N-desmethyl-tamoxifen, and N-desmethyl-4-hydroxy-tamoxifen (endoxifen).

Safety will be assessed by evaluating AEs, vital sign measurements, clinical laboratory test results, 12-lead ECGs, and physical examination findings. In addition, vaginal speculum examinations will be performed, including an assessment of local irritation (in terms of erythema and edema). Women without a history of hysterectomy will undergo transvaginal ultrasounds at screening and at the end of treatment (Day 57).

Following the completion of treatment, participants will attend a follow-up visit on Day 63.

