7.2. Rationale and Discussion of Study Design

The use of estrogen-containing products for the treatment of VVA is contraindicated in women with HR+ breast cancer, due to their capacity to promote tumor growth. There remains a large unmet need for a novel nonhormonal VVA treatment for this subset of cancer patients and survivors, and other women who require or prefer a treatment option that does not contain estrogen. An exploratory study of intravaginal tamoxifen has demonstrated the potential for this SERM, which acts as an estrogen receptor agonist in the vagina and as an antagonist in breast tissue, to improve VVA symptoms (vaginal pH and patient-reported dryness). In addition, plasma concentrations of tamoxifen were considerably lower than those seen with oral administration.

The present study is the first clinical evaluation of DARE-VVA1, a GMP-manufactured tamoxifen vaginal insert intended for self-placement. The study will evaluate 5 parallel groups of 8 patients, randomizing participants to receive DARE-VVA1 at 1 of the 4 dose levels or placebo. The double-blind, placebo-controlled, randomized study is a gold standard for clinical studies, and is considered suitable for the present study where the placebo vaginal inserts are identical to the

DARE-VVA1 inserts. Inclusion of a matched placebo will allow the distinction between adverse effects caused by tamoxifen and those that can be attributed to excipients or to mechanical effects due to the presence of an insert.

The study will be conducted in postmenopausal women with VVA, allowing a preliminary investigation of the PD of the IP in the target population. Eligibility criteria have been designed to exclude participants who might be at risk of the serious, albeit rare, side effects associated with tamoxifen such as thromboembolic effects and endometrial cancer; the short duration of the study will also reduce these risks, which are typically associated with long-term tamoxifen use.¹⁸

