9.7.2 Prohibited Therapies

The following therapies are prohibited both during the study and in the period before the study as shown:

- use of anticoagulant drugs to treat or prevent coagulopathies, thrombophilia, thromboembolic disease, or transient ischemic attack
- radiation treatment to the pelvis
- vaginal hormonal products (rings, creams, gels, tablets, capsules) (within 4 weeks prior to Day 1)
- transdermal estrogen products (within 4 weeks prior to Day 1)
- oral estrogen therapy (within 8 weeks prior to Day 1)
- estrogen-alone injectable drug therapy (within 12 weeks prior to Day 1)
- estrogen pellet therapy (within 6 months prior to Day 1)
- thyroid hormone replacement therapy is prohibited unless the participant has been on a stable dose for > 6 months, and is euthyroid based on a normal, sensitive immunoassay for TSH
- SERMS or AIs (within 6 months prior to Day 1)
- anabolic or other steroids (including hormonal creams such as testosterone) (within 4 weeks prior to Day 1)
- corticosteroids, > 5 mg/day prednisone or equivalent, for more than 4 weeks within 4 weeks prior to Day 1
- investigational drug (within 30 days prior to screening) or non-drug eluting medical device (within 15 days prior to screening)

The following therapies are prohibited during the study:

- intravaginal products (e.g., Femring® [estradiol acetate vaginal ring], ESTRING® [estradiol vaginal ring]) or medication, OTC or prescription

NOTE: the use of vaginal lubricants is permitted, but not within 6 hours of administration of the IP

- consumption of St John's Wort (*hypericum perforatum*) and grapefruit, Seville (bitter) orange, and pomelo fruit/juice/preserves
- the following CYP3A4/5 inducers and CYP2D6 inhibitors are prohibited:

CYP3A4/5 inducers	CYP2D6 inhibitors
Apalutamide (strong), aprepitant, armodafinil	Abiraterone, amiodarone
Bosentan (moderate)	Bupropion (strong)
Carbamazepine (strong), corticosteroids	Celecoxib, cinacalcet (moderate), cobicistat
Dabrafenib	Duloxetine (moderate)
Efavirenz (moderate), encorafenib, enzalutamide (strong), etravirine (moderate)	Fluoxetine (strong)
Lorlatinib (moderate), lumacaftor (strong)	Methadone, mirabegron (moderate)
Modafinil (moderate)	Paroxetine (strong)
Nevirapine	Terbinafine (strong)
Phenobarbital, phenytoin (strong)	
Rifabutin, rifampicin (strong), ritonavir, rufinamide	
Tipranavir	
Vemurafenib	

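### Exclusion 2 is ambiguously worded: it can be read as reaching only anticoagulant drugs, although other sections indicate that a history of thrombotic disease is itself meant to exclude

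*Combined protocol and SAP*

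**What the plan says.** Exclusion 2 reads "A medical history of or use of anticoagulant drugs to treat or prevent coagulopathies, thrombophilia or thromboembolic disease" in the synopsis (Section 2.1) and again in Section 8.2.2. A parenthesis then gives deep vein thrombosis, pulmonary or systemic embolism, stroke and TIA as examples.

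Other sections describe the same exclusion in different terms:

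- Section 5.4 says participants are excluded if they have "a history of coagulopathies, thrombophilia, thromboembolic disease, or significant transient ischemic attack". It mentions no drug.
- Section 7.1 says "Participants will not be eligible if they have a medical history that suggests that they may be at risk of serious side effects of tamoxifen", and its first example is thromboembolic disease.
- Section 7.2 says "Eligibility criteria have been designed to exclude participants who might be at risk of the serious, albeit rare, side effects associated with tamoxifen", and names thromboembolic effects among them.
- Section 9.7.2, the list of prohibited therapies, names "use of anticoagulant drugs to treat or prevent coagulopathies, thrombophilia, thromboembolic disease, or transient ischemic attack".

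**The concern.** Sites decide eligibility from the numbered criteria. In exclusion 2, nothing marks where the object of *medical history of* begins. It may be the diseases at the end of the phrase, or the anticoagulant drugs in the middle. On the second construction, the criterion says nothing about a woman who had a clot, stroke or TIA and never took an anticoagulant.

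The criterion matters because of what the protocol rests on it. Section 5.4 reports that the oral tamoxifen label carries a boxed warning that includes stroke and pulmonary embolism, and a general warning on thromboembolic events. It names the eligibility criteria as one of the steps that reduce risk, alongside the 56-day limit and the lower systemic exposure from vaginal dosing. Safety is a primary objective (Section 6.1), about 3 sites will apply the list (Section 7.4), and there is no data safety monitoring board (Section 12). The exclusion list is also used after enrolment: under Section 8.2, developing an exclusion criterion on study opens the question of discontinuation.

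**Working it through.** No arithmetic applies. The check sets the two constructions of exclusion 2 against the rest of the protocol.

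**The two readings**

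- *Reading A, two grounds:* a history of the listed diseases, or use of anticoagulants to treat or prevent them. A past clot, stroke or TIA excludes, however it was treated.
- *Reading B, drugs only:* a history of taking anticoagulants, or current use of them, for those diseases. A past event never treated with an anticoagulant does not meet the criterion.

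**Step 1: statements of intent.** Section 5.4 makes disease history the ground and attaches no drug condition. Section 7.1 bases ineligibility on medical history and names thromboembolic disease. Section 7.2 says the criteria were designed to keep out women at risk of such effects. Reading A agrees with all three. Reading B conflicts with them.

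**Step 2: usage within the list.** Exclusion 1 has the same unpunctuated form, "A history of or physical examination finding for any significant cardiovascular, renal, pulmonary, neurological and hepatic diseases preventing compliance with this study", and there *history of* must attach to the diseases. Exclusion 5 pairs a history with current endometrial pathology in a similar way. Exclusions 6, 7 and 9 follow the phrase with a condition, for example "A medical history of malignant melanoma". The drug exclusions (14 to 18 and 20 to 22) open with use or administration of the product, and none speaks of a medical history of a drug. All this favours Reading A.

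**Step 3: Section 9.7.2.** It names only drug use, but a list of therapies could name nothing else. It repeats the drug part of exclusion 2 as a complete phrase, which fits Reading A. It does not exclude Reading B.

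**Step 4: would another criterion catch the woman missed under Reading B?**

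| Criterion | Scope | Clearly catches an untreated past clot, stroke or TIA? |
|---|---|---|
| Exclusion 1 | Significant disease, limited to disease that prevents compliance | No |
| Exclusion 3 | Hypertension, certain cardiac drugs, heart failure, recent infarction | No |
| Exclusion 28 | Investigator's opinion that the "participant has any disorder or finding that might interfere with the conduct of the study" | Discretionary |
| Inclusion 13 | Laboratory results, including coagulation | No; it does not address clinical history |

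**Step 5: TIA across sections.** Exclusion 2 lists TIA without a qualifier, as an example of thromboembolic disease. Section 5.4 lists it separately and requires it to be significant. Section 9.7.2 lists it separately with no qualifier. Among these three statements, only exclusion 2 names stroke. This mismatch exists under either reading.

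**The case against.** The strongest reply is that the documents already settle the meaning. Reading A is grammatical, matches the list's own usage, and is confirmed by Sections 5.4, 7.1 and 7.2. Investigators sign that they have read and understood the whole protocol (Section 14.1.2). The study population is described as healthy, coagulation results are screened, and exclusion 28 leaves room for judgement. On this view only a comma is missing.

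Most of that stands. A reader might infer that exclusion 2 covers drugs and not disease history, so that women with past thrombotic events are admitted by the plan. The documents do not support that. It treats the weaker of two readings as the only one, against three sections and the neighbouring criteria. The most that can be said is that such women could be enrolled if the criterion is read as drug-only.

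A reader might also take the oral tamoxifen event rates in Section 5.4 as the size of the problem. They do not measure it. They compare oral 20 mg daily with placebo over a median of 3.5 years, and they say nothing about women with earlier events or about how many could be misclassified. Applied as they stand to 32 women on active drug for 56 days (32 × 56 / 365.25 = 4.9 woman-years), the oral rates for stroke, pulmonary embolism and deep vein thrombosis (1.43 + 0.75 + 1.26 = 3.44 per 1,000 per year) give about 0.017 events. That is small, but it describes the cited trial's population and not the women at issue here.

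Nor does the protocol's judgement that the risks are minimal rest on this criterion alone. Section 5.4 ties that judgement to 56 days of treatment.

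What the reply does not remove is that the operative text has to be interpreted with the help of other sections, and that no other listed criterion clearly serves as a backstop if it is misread. It also leaves the TIA wording unsettled. The criterion is the broader text there, so the mismatch alone admits nobody if sites follow the criterion, but sites are still given two descriptions of one exclusion.

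**Conclusion.** The point holds as an ambiguity in an operative safety exclusion. Exclusion 2 can be read as drug-only. That reading conflicts with Sections 5.4, 7.1 and 7.2, and under it a woman with a past clot, embolism, stroke or TIA never treated with an anticoagulant would not be clearly caught elsewhere. The intended meaning is probably that of Section 5.4. Separately, Section 5.4 and exclusion 2 differ on whether a TIA must be significant.

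Severity is low. No figure can be put on it, because the documents give neither the number of candidates with such a history nor how sites will read the text. The conclusion rests on the wording alone and takes no view on which clinical rule is right.

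**What to change.** Reconcile exclusion 2, in both Section 2.1 and Section 8.2.2, with Sections 5.4, 7.1 and 9.7.2, so that it is unambiguous whether disease history and anticoagulant use are separate grounds for exclusion. If they are, as Sections 5.4 and 7.1 indicate, setting them out as two lettered items removes the doubt. Use one wording for TIA throughout, and make clear whether stroke falls within the summary in Section 5.4. The choice of TIA rule belongs to the sponsor and its medical advisers.

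The cost is a few words in each place, handled under the amendment procedure in Section 14.8. There is no effect on data collection, sample size or analysis. If women have already been enrolled, the medical history taken at screening allows a check of how the criterion was applied.
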